The primary outcome measures are Speech intelligibility measured objectively with HINT (sentences in noise) and DANTALE I (words) and subjectively with the Speech, Spatial and Qualities of Hearing scale questionnaire (SSQ-12). Secondary outcomes are patient reported Health-Related Quality of Life (HRQoL) scores assessed with the Nijmegen Cochlear Implant Questionnaire (NCIQ), the Tinnitus Handicap Inventory (THI) and Dizziness Handicap Inventory (DHI). Third outcome is listening effort assessed with pupil dilation during HINT

In conclusion, the purpose is to improve clinical decision-making for CI candidacy and optimize bimodal solutions.

Ethics and Dissemination

This study protocol was approved by the Ethics Committee Southern Denmark project ID S-20200074G. All participants are required to sign an informed consent form.

This study will be published upon completion in a peer-reviewed publications and scientific conferences.

Trial Registration Number: NCT04919928 (ClinicalTrials.gov)

Strengths and Limitations of This Study

- The study uses comprehensive measures of self-reported outcomes as well as objective tests of speech intelligibility.
- Listening effort controlled with pupillometry during objective tests of speech intelligibility.
- Open label RCT (blinding is not possible due to visibility of the CI).
- Possible large drop rates if new HAs improve speech intelligibility to an extent that CI treatment is rejected or postponed.

Introduction

Background

Cochlear implants (CIs) have been used to restore hearing in individuals with severe to profound sensorineural hearing loss. Initially, most patients receiving a cochlear implant were profoundly deaf in both ears. (1, 2) However, recently it has become more common to implant patients with significant residual hearing in the affected ear, as well as in patients with asymmetric hearing loss and single-sided deafness, with significant residual hearing or normal hearing on the contralateral side.(3, 4) A CI in one ear and a HA in the other ear can provide enhanced hearing performance in patients with asymmetrical hearing.(5, 6) The combination of CI and HA is referred to as bimodal hearing or bimodal solution.(7)

CI Candidacy

In the UK, The National Institute for Health and Care Excellence (NICE) have listed guidelines for cochlear implantation and recommends that unilateral CI is offered to patients

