with severe to profound deafness who do not receive adequate benefit from acoustic hearing aids. Severe to profound deafness is defined as pure-tone audiometric threshold ≥ 80 dB HL at 2 or more frequencies (500 Hz, 1,000 Hz, 2,000 Hz, 3,000 Hz and 4,000 Hz). Another criteria is that SIS< 50% in the ear considered for implantation and in best aided condition SIS $\leq 60\%$ (8).

The Danish CI candidacy criteria consists of SIS (without HAs, measured with headphones) $\leq 45\%$ and a SIS $\leq 65\%$ (in best aided condition) in the ear considered for implantation using DANTALE I monosyllabic word-lists.(9) Additional testing to evaluate speech understanding is assessed by HINT.(10, 11)

The recommendation for a CI might be less clear for patients with asymmetric hearing because they may not fall into the traditional referral criteria but would likely benefit from a CI. It is therefore necessary to establish more evidence to support the effectiveness of bimodal CI+HA versus HAs in patients with asymmetric hearing.

Bimodal Solution vs. Bilateral HAs

Normal hearing listeners (NH) benefit from listening with two ears, which help them understand speech in noise and identify sound location.

Benefits from listening with two ears include: head shadow effect, binaural summation, binaural squelch, localization and spatial release from masking.(12-15)

Patients with hearing loss often do not have these benefits, and they are often not accessible to CI patients. (15)Many bimodal CI and HA users are missing these benefits because the devices are unsynchronized.(16)

Until now it is unknown when to introduce the bimodal solution and making sure that patients are well-fitted with hearing aids when they are given the candidacy assessment.

The question is if the bimodal benefits are bigger than the bilateral hearing aid condition when they are well fitted?

This study will therefore support and strengthen the preoperative clinical decision to recommend a bimodal solution with a CI and a HA versus the continuous use of bilateral HAs. This may offer the patient faster and more effective treatment because delaying the surgery may not be beneficial.

Patient-Reported Outcome Measures

Benefits of the CI are measured subjectively with Patient-Reported Outcome Measures (PROMs) as SSQ12, NCIQ, THI and DHI.(17-24)

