This study is a prospective randomised controlled trial based on a single centre conducted in Odense University Hospital, Denmark. The study started 01/02/2022 and is expected to end 30/07/2024. It was successfully registered at ClinicalTrials.gov with registration number: NCT04919928.

This study has been approved at Research Ethics Committee Southern Denmark (Projekt-ID: S-20200074G) 21st August 2020 to 31st December 2024.

Study Population

Sixty participants with bilateral hearing-loss and asymmetric speech identification scores referred for CI surgery will be included (Figure 1).

Inclusion Criteria

- Adults >18 years old.
- Fluent in Danish, including reading and writing
- Acquired post-lingual deafness
- Use of bilateral HAs for at least one year prior to evaluation for cochlear implantation candidacy. This to ensure, that both ears have received auditive stimulation
- PTA > 40 dB HL in the ear considered for CI implantation and PTA \geq 40 and \leq 70dB HL in the contralateral ear in best aided condition, in quiet and in noise and in free field.

- SIS <70% in best aided condition in the ear considered for CI implantation and SIS $\geq 30\%$ and $\leq 70\%$ in best aided condition in the contralateral ear, in quiet and in noise and in free field.

Exclusion Criteria

- Vestibular loss in the ear not considered for CI implantation
- Surgical issues interfering with the site of implantation or anatomical contraindications such as cochlear malformations, which will be determined using MRI or CT-scans.
- Auditory nerve lesions.
- Central auditory pathway pathologies.
- Otosclerosis.
- Single sided deafness (SSD).

Setup

A timeline of the study is shown in (Figure 2).

All enrolled participants will be tested with audiology and v-HIT to determine hearing thresholds and status of balance function during the first visit. Patients will receive new replacement HAs. These HAs will be fitted during the second visit and if necessary refitted at every visit in the clinic throughout the study. The baseline measurements will be conducted when both groups have used the new replacement HAs to ensure acclimatisation. The measurements are SIS in quiet and in noise with a signal-to-noise ratio (SNR) of 0dB using DANTALE I speech material. The speech and masking white noise

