Secondary outcomes will be analysed analogously in a constrained linear mixed model adjusting for randomisation strata. Model validation checks will be undertaken as described above, switching to bootstrapping the standard errors when model assumptions are rejected.

Covariates such as age and gender will be included in all models.

Sensitivity analysis

Inclusion is performed conditional on Pure Tone Average (PTA) (from 0.5 to 4 kHz) $PTA > 40 \text{ dB HL}$ and SIS $<50\%$ in the ear considered for CI implantation and $<70\%$ in the best-aided condition which may lead to a truncation effect in the distribution of baseline measurements. To address this, an analysis of covariance (ANCOVA) model conditioning on the baseline will be used to obtain a sensitivity analysis estimate for the main outcome.(40)

The statistical analysis plan is attached as “supplementary file” along with the Data Description listed in Appendix A.

Patient and Public Involvement

A focus-group interview was established with six cochlear implant patients. The patients commented on their decision to transition from HA to CI. Based on the feedback from the focus group, the research questions were developed.

The patients also reported problems with adjustments of the CI, when meeting the audiologist for CI adjustment controls.

Ethics and Dissemination

Ethics approval for the conduct of this study was obtained from the Ethics Committee Southern Denmark, 21st August 2020 project ID S-20200074G.

The project is approved by the Danish Data Protection Agency (file no. 20/22868) in Region South Denmark.

All participants are treated according to current clinical standards regardless of the randomised study participation. The participants are volunteers and can at any moment withdraw their participation in the study without affecting their current or future treatment rights.

The Informed Consent form will be found online as an online supplementary file and it will be signed by all participants willing to participate the study and stored in their electronic journals in Department of Audiology, Odense University Hospital. All patients are given both oral and written information about the study.

Results

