Secondary outcomes will be analysed analogously in a constrained linear mixed model adjusting for randomisation strata. Model validation checks will be undertaken as described above, switching to bootstrapping the standard errors when model assumptions are rejected. Covariates such as age and gender will be included in all models.

Sensitivity analysis

Inclusion is performed conditional on Pure Tone Average (PTA) (from 0.5 to 4 kHz) PTA > 40 dB HL and SIS <50% in the ear considered for CI implantation and <70% in the best-aided condition which may lead to a truncation effect in the distribution of baseline measurements.

To address this, an analysis of covariance (ANCOVA) model conditioning on the baseline will be used to obtain a sensitivity analysis estimate for the main outcome. (2)

The statistical analysis plan is attached as “supplementary file” along with the Data Description listed in Appendix A.

2)

Liu, Guanghan F., Kaifeng Lu, Robin Mogg, Madhuja Mallick, and Devan V. Mehrotra. 'Should Baseline Be a Covariate or Dependent Variable in Analyses of Change from Baseline in Clinical Trials?: ANALYSES OF CHANGE FROM BASELINE IN CLINICAL TRIALS'. *Statistics in Medicine* 28, no. 20 (10 September 2009): 2509–30. <https://doi.org/10.1002/sim.3639>.

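### The speech-score entry limit for the ear to be implanted differs between the inclusion list and the sensitivity text, and the number randomised is given as both 60 and 72

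*SAP*

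**What the plan says.** **Entry limit.** For the ear to be implanted, the Protocol's Inclusion Criteria require "SIS <70% in best aided condition in the ear considered for CI implantation". For the other ear they require a score from 30% to 70%, "in best aided condition in the contralateral ear, in quiet and in noise and in free field". The Sensitivity analysis sections of the Protocol and the SAP describe entry differently. The Protocol's opens with "Inclusion is performed conditional on Pure Tone Average (PTA", and both go on to name "SIS <50% in the ear considered for CI implantation and <70% in the best-aided condition". They give no test condition for the 50% and do not mention the contralateral ear.

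**Number randomised.** The Protocol's Abstract and Study Population say sixty, its Control Group and Intervention Group sections say thirty each, and the SAP's sample size entry says 60. The Protocol's Power calculation derives 30 per arm and then adds six per arm (20%) for drop-out.

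**Missing data.** Under Strengths and Limitations the Protocol foresees "Possible large drop rates if new HAs improve speech intelligibility to an extent that CI treatment is rejected or postponed". Item 3 of Definition of Analysis Sets, in both documents, promises sensitivity analyses for departures from the main analysis's missing-data assumption. The only one specified is that "an analysis of covariance (ANCOVA) model conditioning on the baseline will be used to obtain a sensitivity analysis estimate for the main outcome", and its stated purpose is to deal with truncation caused by the entry limits.

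**The concern.** Two current sections each claim to state the entry rule, and they state different ones. The trial's aim is to inform candidacy decisions, so the speech-score limit determines which patients the result informs. It also determines whether a monitor can confirm that a given participant qualified. The scores are measured with DANTALE I, which is also a primary outcome, so the limit acts on the scale of a primary outcome. The truncation argument for the ANCOVA cites a limit that is not in the inclusion list and leaves out limits that are.

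The sample size matters for a different reason. If 60 is the number randomised, the drop-out allowance described in Power calculation does not exist, and the stated power holds only if nobody is lost.

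**Working it through.** **1. The entry rule side by side.** The PTA limit for the ear to be implanted (above 40 dB HL) is the same in both places. Only the speech score differs. The Protocol's CI Candidacy section describes two existing rule forms that the 50%/70% pair might follow, which gives three readings.

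- *Unaided limit plus aided limit, same ear.* This is the form introduced by "The Danish CI candidacy criteria consists of SIS (without HAs, measured with headphones", which pairs an unaided limit with a best-aided limit in the same ear. The 70% figures then agree, and the inclusion list omits the 50% criterion. This is the most plausible reading.
- *Ear limit plus a best-aided limit not tied to that ear.* This is the UK form: "Another criteria is that SIS< 50% in the ear considered for implantation and in best aided condition SIS", followed by its own figure. The inclusion list then omits the 50% criterion and attaches the 70% to a different condition.
- *Both limits in the same ear and the same aided condition.* The 50% then governs. A patient scoring at least 50% but below 70% qualifies under Inclusion Criteria and not under Sensitivity analysis.

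Under all three, the sections describe different populations, and the sensitivity text omits the contralateral 30% to 70% range.

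**2. The stated group size.** Inputs from Power calculation and Table 1: SSQ-12 difference 1.4, SD 1.9, power 0.80, significance level 0.05 (taken as two-sided).

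- Standardised difference: 1.4 / 1.9 = 0.737.
- Two-sample t-test: n = 29.90, rounded up to 30 per arm. This reproduces the stated figure. The normal approximation gives 29.

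**3. The two totals.** 30 + 30 = 60. With the allowance, (30 + 6) × 2 = 72, which is 12 / 60 = 20% more recruitment.

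**4. Unadjusted power for SSQ-12** (same t-test):

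- 36 per arm (72 randomised, none lost): 0.869.
- 30 per arm (72 randomised and six lost per arm, or 60 and none lost): 0.801.
- 24 per arm (60 randomised and six lost per arm): 0.705.

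**5. With baseline adjustment.** The planned constrained mixed model uses the baseline value. As an approximation, replace the SD by 1.9 × √(1 − r²), where r is the baseline to follow-up correlation. The documents do not give r, so 0.3 to 0.7 is an assumed range. At 24 per arm:

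- r = 0.3: SD 1.812, standardised difference 0.772, power 0.745.
- r = 0.5: SD 1.645, standardised difference 0.851, power 0.823.
- r = 0.7: SD 1.357, standardised difference 1.032, power 0.938.

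**6. What the ANCOVA tests.** Fitted to observed outcomes, both the mixed model and the ANCOVA rely on missingness being explained by what was observed. If they agree, that says nothing about departures from this assumption, so the ANCOVA does not deliver item 3.

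**The case against.** *The inclusion list is the operative text, and the sensitivity section is only background.* This stands as far as the analysis goes: the ANCOVA can be run under either rule, and no step depends on the number quoted. But the background text asserts what inclusion was conditional on, and it does so in both documents, so a reader cannot tell which rule was applied.

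*The 50% is probably an unaided score.* It may be, but the inclusion list would then be one criterion short. The population figure is not shown and Appendix A is not among the documents reviewed. Either might clarify the rule, but the conflict in the text would remain.

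*Power calculation reads naturally as 60 evaluable plus 12.* That is a fair reading of that section. However, the Abstract and Study Population describe sixty as enrolled or included, and the SAP gives 60 without qualification.

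*The loss of power is overstated.* In part this stands. The figure of 0.705 applies to the unadjusted test behind the stated 30 per arm. Adjusted power is above 0.80 at r = 0.5 and 0.7, and below it at r = 0.3.

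*Missing data are already handled.* The plan does follow participants who withdraw from treatment and does promise sensitivity analyses. Randomisation also comes after the month with new hearing aids, so some refusals will fall before allocation. What remains is a missing method, which is a minor point.

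**Conclusion.** The mismatch in the entry limit is certain from the text and should be corrected. It affects the population described and the audit of entry. The mismatch between 60 and 72 is equally plain. If 60 is the total and six per arm are lost, SSQ-12 power is 0.705 unadjusted, or about 0.75 to 0.94 with baseline adjustment over the assumed correlations. If 72 are randomised, the stated 0.80 survives that loss. The unspecified method under item 3 is secondary.

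A reader might infer three stronger conclusions that the documents do not support.

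- *That the entry limit biases the treatment effect.* Both arms are randomised from whatever population was admitted, so the comparison between them is unaffected.
- *That a share of participants was wrongly admitted.* The documents give no score distribution, and under the most plausible reading the 50% refers to a different test condition, so no share can be calculated.
- *That only refusal of surgery in the intervention arm can distort the result.* Controls are also due an implant after four months of hearing-aid use. Neither the drop-out warning nor the permission to leave under HA Fitting is confined to one arm. Loss of controls who do well with hearing aids could bias the comparison too, and without refusal rates by arm neither the size nor the direction can be stated.

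**What to change.** - **Entry limit.** The sponsor should reconcile Inclusion Criteria with the Sensitivity analysis sections of both documents. There should be one rule, stating for each limit the ear, aided or unaided, and quiet or noise. The truncation rationale should then cite the same limits, including those for the contralateral ear. The study began on 01/02/2022 and this version is dated 21 August 2022, so the text should also record which rule was applied to anyone already screened.
- **Number randomised.** State one figure in the Abstract, Study Population, the two group sections, Power calculation and the SAP. If it is 60, remove the allowance and restate power after drop-out, giving the correlation assumed. If it is 72, recruitment rises by 20% over 60.
- **Missing data.** Name a method for item 3. A delta-adjusted analysis would serve: impute missing outcomes under the main model, shift them upwards and downwards in each arm separately, and report where the conclusion changes.

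The cost is wording in two documents and one small extra analysis. Only adopting 72 would add participants.

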REDCap will also be used to send out the questionnaires to the participants' online mailbox (called Eboks in Denmark) throughout the study (see timeline (Figure 2)) and automatically save the data.

Participants will have the opportunity to return to their original HAs if they prefer to do so after one-month of acclimatisation.

Control Group

Thirty patients, who will be age-matched, randomised and allocated to the control group HA+HA will continue the use of the new replacement HAs for another three months (total four months of new replacement HA+HA use), serving as the delayed intervention control group.

Intervention Group

Thirty patients, who will be age-matched, randomised and allocated to the intervention group CI+HA will undergo surgery as soon as possible after the HA acclimatisation period.

HA Fitting

The participant will receive either Phonak (Phonak Link M) or GN (ReSound LiNX Quattro or Resound ENZO Q) based on their personal preference. Both these HA models can be fitted with a CI by Advanced Bionics and Cochlear, respectively.

The HAs will be fitted according to NAL-NL2 procedures prescriptive fitting formula, which optimizes audibility in the bimodal solution(2) and will be verified with REM (Real Ear Measurement) to ensure that the HA is providing adequate gain and then further adjusted for comfort based on patient feedback.(35)

The new HAs will be prescribed to the patients free of charge and future service will also be free of charge.

Participants can drop out of the study if they do not want CI surgery. Collected data will be analysed if the patient still consents.

CI fitting

The CI will be selected depending on the participant's HA selection; that is, the CI that is compatible with the HA will be selected in order to ensure the most optimal bimodal fitting. One-month post-surgery, the CI will be activated according to the settings and stimulation strategy based on patient's feedback. The CI will then be fitted with the HA according to the bimodal fitting formula allowing the HA to keep the NAL-NL2 fitting along with the wireless connection with the CI. (36, 37)

Patients hearing thresholds will be tested on CI activation day. The residual hearing will not be stimulated in this study.

All participants are offered standard rehabilitation with a speech therapist, including three visits a week up to 10 weeks following the initial fitting.

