Power calculations with a power of 0.8 with a significance level of 0.05 have been made with STATA IC-15 using standard deviations for the HINT test and expected effect size (38) the NCIQ(18), and the SSQ (internal communication with BEAR (Better Hearing Rehabilitation) study on hearing aid use in Denmark) (Table 1). An estimated within participant standard deviation from the BEAR study of 1,9 in an HA population using the

SSQ-12 is used to calculate the sample size. A difference of 1.4 will require 30 participants in each arm. The effect size is expected to be larger in the CI group which will lower the number of required subjects even further.

Based on this, 30 participants must be enrolled in each arm. Additional six patients (20%) in each arm will be enrolled in the study to account for dropouts.

Test	SD pre	SD post	Expected difference between the two treatment arms	Minimum required group size
1. HINT	6.3%	6.3%	5%	26
2. NCIQ – basic sound perception	14.4	23.5	53	4
2. NCIQ	13.4	19.6	34	6
2. NCIQ – speech perception	18.8	17.8	17	20
2.NCIQ Self-esteem	20.1	16.4	22	13
2.NCIQ Activity	23.0	15.9	27	10
2.NCIQ Social Interactions	19.8	14.5	25	9
3. SSQ Total	1.9	1.9	1.4	30

Table 1: Power calculations for the desired tests. Estimated within participant standard deviations (SD pre and SD post) with expected difference and the calculated required group size.

Definition of Analysis Sets

Strategy for intention to treat analysis with incomplete observations.(39)

1. Attempt to follow-up on all randomised participants, even if they withdraw from allocated treatment.
2. Perform a main analysis of all observed data that are valid under a plausible assumption about the missing data.
3. Perform sensitivity analyses to explore the effect of deviations from the assumption made in the main analysis.
4. Account for all randomised participants, at least in the sensitivity analyses.

Analysis specification

A constrained linear mixed model is used to analyse the outcome.

The model will include randomisation group (CI+HA / HA+HA) and time (baseline/follow-up) and their interaction as fixed effects along with the threshold strata that were used in stratifying the randomisation. The model is constrained so that the mean at baseline agrees across the two treatment groups adjusted for threshold stratum, which is reasonable due to the randomisation of implant fitting. Patient ID will be included as a random effect to account for the repeated measurements.

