Patient reported outcomes scores assessed with the Nijmegen Cochlear Implant Questionnaire (NCIQ), The Tinnitus Handicap Inventory (THI) and Dizziness Handicap Inventory (DHI).

Third Outcome

Listening effort assessed with pupil dilation with HINT.

Definition of treatment variables

Treatments are HAs and CI-surgery assigned by randomisation. The primary comparison will be between the CI+HA and HA+HA groups.

Covariates used in analyses

Stratified randomisation for thresholds of the ear to be implanted.

Definition of effect size/parameter of interest

Primary effect size:

Objective outcome: Mean difference in HINT in quiet and in noise between intervention group (HA+CI) and control group (HA+HA) at 3, 6 and 12 months follow-up post- bimodal CI+HA-fitting and 3 months post-HA-fitting respectively.

Subjective outcome: Mean difference in SSQ-12-scores at 3, 6 and 12 months follow-up post- bimodal CI+HA-fitting and 3 months post-HA-fitting respectively

Definition of Analysis Sets

Strategy for intention to treat analysis with incomplete observations.1)

1. Attempt to follow-up on all randomised participants, even if they withdraw from allocated treatment.
2. Perform a main analysis of all observed data that are valid under a plausible assumption about the missing data.
3. Perform sensitivity analyses to explore the effect of deviations from the assumption made in the main analysis.
4. Account for all randomised participants, at least in the sensitivity analyses.

1)

White, Ian R., Nicholas J. Horton, James Carpenter, and Stuart J. Pocock. 2011. 'Strategy for Intention to Treat Analysis in Randomised Trials with Missing Outcome Data'. *BMJ* 342 (February): d40. <https://doi.org/10.1136/bmj.d40>.

Analysis specification

A constrained linear mixed model is used to analyse the outcome.

The model will include randomisation group (CI+HA / HA+HA) and time (baseline/follow-up) and their interaction as fixed effects along with the threshold strata that were used in stratifying the randomisation. The model is constrained so that the mean at baseline agrees

across the two treatment groups adjusted for threshold stratum, which is reasonable due to the randomisation of implant fitting. Patient ID will be included as a random effect to account for the repeated measurements.

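### Does the SAP leave dropout among people who decline the implant untested, having promised sensitivity analyses for missing data?

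*SAP*

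**What the plan says.** The SAP, under Definition of Analysis Sets, sets out four steps; the protocol has the same list. The first is to "Attempt to follow-up on all randomised participants, even if they withdraw from allocated treatment". The second is a main analysis of all observed data under a plausible missing-data assumption, which is not named. The third is to "Perform sensitivity analyses to explore the effect of deviations from the assumption made in the main analysis", and the fourth to "Account for all randomised participants, at least in the sensitivity analyses".

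The main model is a constrained linear mixed model with a random effect for patient. The SAP's Sensitivity analysis section holds one item, an "analysis of covariance (ANCOVA) model conditioning on the baseline will be used to obtain a sensitivity analysis estimate for the main outcome". Its stated reason is that the entry criteria may truncate the baseline distribution.

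The SSQ-12 effect is defined as "Mean difference in SSQ-12-scores at 3, 6 and 12 months follow-up post- bimodal CI+HA-fitting and 3 months post-HA-fitting respectively". CI-arm outcomes are therefore timed from bimodal fitting and control outcomes from hearing-aid fitting.

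On dropout, the protocol lists among its limitations "Possible large drop rates if new HAs improve speech intelligibility to an extent that CI treatment is rejected or postponed". Under HA Fitting it says: "Participants can drop out of the study if they do not want CI surgery. Collected data will be analysed if the patient still consents". Under Power calculation it says: "Additional six patients (20%) in each arm will be enrolled in the study to account for dropouts".

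**The concern.** Steps three and four are a commitment, and the section where a reader would expect it to be met contains only the ANCOVA. Without imputation, that model uses only participants with a follow-up score, and it does not vary the missing-data assumption. It satisfies neither step.

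The protocol itself expects people to leave because their new hearing aids work well, which makes the dropout related to outcome. If it falls mainly on the CI arm, a model that assumes missingness depends only on observed data could be biased. A CI-arm participant who declines surgery also never reaches the fitting visit from which the SAP counts outcome time.

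At stake is how far the reported effect could lie from the effect in everyone randomised, and whether close agreement between ANCOVA and mixed model might be taken as evidence that dropout does no harm.

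**Working it through.** **Plan's own figure.** SSQ-12 difference 1.4, SD 1.9, significance level 0.05 (taken as two-sided), power 0.80, all from Power calculation. Normal approximation: n = 2 × (1.96 + 0.84)² × 1.9² / 1.4² = 28.9, so 29 per arm. The two-sample t-test gives 29.9, so 30, as stated. Adding six gives 36 per arm.

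**Assumptions for the illustration.** The documents give no rate of declining surgery, so the allowance of six per arm is used. Decliners get no CI effect, everyone else in the CI arm gains 1.4, and the baseline/follow-up correlation is 0.3 to 0.7. Results are for 36 per arm, with 30 per arm in brackets. Stratum, age and sex are left out.

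**All-randomised effect.** 1.4 × 30/36 = 1.17 (1.4 × 24/30 = 1.12).

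**Simulation.** Bivariate normal scores; constrained-baseline random-intercept model with known covariance, keeping participants who have baseline data only; ANCOVA on those with follow-up. Thousands of replicates per case; repeat runs agree to about 0.01.

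| Case | Main model, 36 per arm | Main model, 30 per arm |
|---|---|---|
| No decliner measured, best hearing-aid responders decline, controls complete | 0.89–1.12 | 0.81–1.08 |
| No decliner measured, random or baseline-driven, controls complete | about 1.40 | about 1.40 |
| Best responders lost from both arms, none measured | 1.38–1.41 | 1.38–1.41 |
| Five of six decliners measured, any of the three selection rules, controls complete | 1.12–1.21 | 1.07–1.17 |
| All-randomised effect | 1.17 | 1.12 |

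In the first two cases the ANCOVA differs from the main model by at most 0.03 points, so it is not a test of dropout.

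**Hand check of the fourth row.** With random decliners and five of six measured, 30 of the 35 measured CI-arm participants carry the effect: 1.4 × 30/35 = 1.20 (1.4 × 24/29 = 1.16). Both lie in the simulated ranges.

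**Reading the table.** The first row combines three conditions: nobody who declines is measured, controls are complete, and declining depends on a future hearing-aid score. The plan departs from the first two. Step one attempts follow-up after withdrawal from allocated treatment, and the dropout allowance is for each arm. Losing the best responders from both arms removes the downward bias. The remaining distance from 1.40 to 1.17 then arises because decliners are unmeasured: 1.40 is the effect had all received their assigned treatment, 1.17 the effect in all randomised.

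The third condition is also strong. Surgery follows the acclimatisation period as soon as possible, so the choice is normally made before the follow-up score exists. Baseline is measured after the new aids have been worn, so early benefit is at least partly in the model. Some satisfied users may also leave in the month before randomisation and would create no missing randomised data.

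**Timing of decliners.** The effect definition is a contrast, not a visit schedule. The protocol refers to Figure 2 for the timeline, including when questionnaires are sent. SSQ-12 reaches participants through an online mailbox, so collecting it does not depend on CI activation. Figure 2 and Appendix A are not in the text reviewed, so no contradiction can be shown.

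**The case for a change.** The strongest case for a change is that the cited strategy is a set of headings to be completed, and the SAP is where to complete them. The trial is open label, so choosing a missing-data method after seeing who declined would invite doubt. Naming the assumption and a method such as delta-adjusted multiple imputation would cost little. Under the unfavourable assumptions the shifts needed are not small: (1.17 − 1.40) / (6/36) is about −1.4 points for random or baseline-driven decliners, and (1.17 − 0.90) / (6/36) is about +1.6 points when the best responders decline and the correlation is 0.3.

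The textual part stands: the assumption and the method are absent, and the ANCOVA does not replace them. The timing part stands only in that the SAP's effect definition is silent on decliners.

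The rest carries less weight. A likelihood-based mixed model on all observed data is ordinarily valid under missing at random, so the assumption can be read from the model. Several sensitivity methods would honour steps three and four, and the SAP already obliges the analyst to use at least one that accounts for everyone randomised. The risk of misreading the ANCOVA is speculative, because the SAP ties it to truncation and nowhere presents it as a dropout check.

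**Conclusion.** No change to the plan is needed. The SAP commits to following people who leave their allocated treatment, to varying the missing-data assumption, and to accounting for all randomised participants. What it lacks is the choice of technique, which a competent analyst fills within those commitments.

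With 36 per arm and the plan's follow-up mostly achieved (five of six decliners measured), the main model lies within about 0.05 SSQ-12 points of the all-randomised effect: 1.12 to 1.21 against 1.17. With 30 per arm it is 1.07 to 1.17 against 1.12. The larger gaps, down to 0.89 or up to 1.40 against 1.17, arise when follow-up of decliners fails altogether; the low end also needs complete controls and selection on a future score. All these figures rest on an assumed six decliners with no CI effect, an effect of 1.4, SD 1.9 and correlations of 0.3 to 0.7. A much higher rate of declining without follow-up would make the choice of sensitivity method matter more, but the documents give no such rate.
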